The Close Collaboration with Parents training program has been developed in Turku University Hospital, Finland. It is a structured and comprehensive training program for neonatal staff aiming to support parenthood and parental involvement in neonatal intensive care. The program addresses staff attitudes by reflection and exercises. The program has been shown to improve implementation of family-centered care in the varying contexts of neonatal intensive care units in both regional hospitals and university hospitals. After the completion of the training program, parents spent more time with their child during hospitalization.(17) Nurses reported that the training program strengthened the family-centered care culture and that the program enforced the role of the parents as primary caregivers.(18,19) Breast feeding was commenced on average three weeks earlier than before the training program, skin-to-skin care was commenced earlier and the amount of skin-to-skin care increased. The weight gain of premature infants improved by 44.5%, and the mothers of very preterm infants suffered from fewer depressive symptoms.(20,21)

It is imperative to study the economic impact of extensive, resource-demanding interventions that affect a whole neonatal unit. The Close Collaboration with Parents training program has so far been implemented in 11 neonatal units in Finland. In addition, four units have changed to single-family room architecture between 2014 and 2019. The national health care registers kept by the Institute for Health and Welfare contain a fully population-based dataset comprising all newborn infants (Medical Birth Register), hospitalizations and outpatient visits (Hospital

Discharge Register). These data are available since 1987, and enable retrospective research on the health and care of newborn infants. In Finland, we currently have a unique opportunity to study the effects of both a family-centered care intervention and single-family room architecture in more controlled circumstances than in previous studies: the interventions have been performed systematically throughout the country; societal support such as paid parental leave and universal access to health care grant all parents the same opportunities to participate; the register data are comparable for all units; and preterm infants can be studied as a separate group.

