## **Methods**

The study population will consist of all newborn infants born from January 1st 2006 to December 31st 2020, who have needed care in a neonatal unit immediately after birth. These infants will be identified from the Hospital Discharge Register. Data on vital background data, birth details, diagnoses, length of stay, growth parameters and outpatient visits will be obtained from the Hospital Discharge Register and the Medical Birth Register. These data will be linked through the infants' personal identification codes, which will be replaced by a pseudonymized ID-number before delivering the data to the research group. Planned subgroup analyses will be done for preterm infants and for infants with significant congenital anomalies.

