### **Description of the interventions: Two interventions are studied (Figure 1)**

- Close Collaboration with Parents-training program in 11 neonatal units
- Adoption of single-family room architecture in 4 neonatal units
- Control group: Infants cared for in the 10 neonatal units where neither of the interventions have been implemented.

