### Outcomes:

The *primary* outcome is the length of stay during the initial hospitalization to neonatal care. Comparisons will be made between infants cared for in intervention units and those cared for in non-intervention units.

*Secondary* outcomes are:

Corrected gestational age at discharge

The amount of outpatient visits after discharge during the first year of life

Growth parameters (weight, length, head circumference) at discharge compared to national standards

Change in growth parameters from birth to discharge

Cost effectiveness (according to hospitalization cost analyses carried out by the Institute for Health and Welfare)

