### Statistical analysis:

The planned analyses include a linear mixed model-approach to account for the effect of unit, degree of prematurity and intervention. Variables that will be considered for inclusion into the model are gestational age at birth, mode of delivery, birth weight z-score, plurality, neonatal morbidities, and receipt of antenatal steroids.

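### The plan has no calendar-time term and no check that adopting and never-adopting units moved in parallel before adoption, so a pre-existing divergence in length of stay would be counted as an intervention effect.

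*Combined protocol and SAP*

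**What the plan says.** - **Outcome and contrast (Outcomes).** "The *primary* outcome is the length of stay during the initial hospitalization to neonatal care". The contrast is "Comparisons will be made between infants cared for in intervention units and those cared for in non-intervention units". No before/after element is stated.
- **Model (Statistical analysis).** A "linear mixed model-approach to account for the effect of unit, degree of prematurity and intervention". The candidate covariates describe the infant, the delivery and perinatal care. Year of birth is not among them.
- **Cohort (Methods).** "all newborn infants born from January 1 st 2006 to December 31 st 2020", which is 15 birth-years.
- **Exposure (Background).** "four units have changed to single-family room architecture between 2014 and 2019". For training: "The Close Collaboration with Parents training program has so far been implemented in 11 neonatal units in Finland". The readable text gives no training dates.
- **Controls (Description of the interventions).** "Infants cared for in the 10 neonatal units where neither of the interventions have been implemented".
- **Claim (Background).** The setting is said to allow study "in more controlled circumstances than in previous studies".

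The readable text does not say how units came to train or rebuild. It mentions no pre-adoption comparison, parallel-trends check or adopter-specific slope.

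**The concern.** Without random allocation, units that took up training or rebuilt may have been on a different path in discharge practice before they did so. A unit effect removes a stable difference in level between units. A birth-year effect, which the plan does not list, would remove a trend shared by all units. Neither removes a difference in slope between adopters and the rest. Adoption comes later in the series, so a difference in slope loads onto the intervention term.

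The study is meant to inform resource allocation (Meaning and potential implications), and the Background criticises earlier work because it could not support causal conclusions. A reader of the planned output could not tell a divergence that began before adoption from a change caused by adoption. The data to examine this are already in the cohort.

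**Working it through.** The plan states no effect size, power, standard deviation or mean stay, so there is no figure of its own to reproduce. The check asks what the intervention term returns when the true effect is zero and adopters drift by d days per year relative to the others.

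**Inputs from the documents.** Birth-years 2006-2020 (15); 4 room units converting within 2014-2019; 11 training units; 10 never-adopting units. Births in 2006-2013 give 8 full years before the earliest possible room conversion.

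**Assumptions.** The intervention term switches on in the unit's adoption year, a reading favourable to the plan, which does not say so. Noise-free unit-by-year means are fitted by least squares with unit fixed effects, as a stand-in for the mixed model. Room conversions are placed in 2014, 2016, 2017 and 2019, and the 11 training dates are spread over 2010-2019.

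**Step 1: listed terms (unit and intervention).** Number the years 0 to 14 and let a unit adopt after k years. The drift averages d(k − 1)/2 before adoption and d(k + 14)/2 after it. The difference is d[(k + 14) − (k − 1)]/2 = 15d/2 = 7.5d. This holds for every k, so the spurious effect is 7.5d whatever the dates. A trend common to all units does the same: −0.1 day per year everywhere gives −0.75 day.

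**Step 2: add birth-year effects.** The common trend now drops out (0.00). The differential trend does not:

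| Adoption pattern (assumed) | Spurious effect |
|---|---|
| All adopters in one year (2014 or 2019) | 7.50d |
| Rooms in 2014, 2016, 2017, 2019 | 6.78d |
| 11 training units over 2010-2019 | 5.48d |

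**Step 3: convert to days.** Take a divergence of 1% of mean stay per year (assumed), with birth-year in the model. The documents give no mean stay, so a range is shown.

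| Mean stay (assumed) | d (days/year) | Rooms, 6.78d | Training, 5.48d |
|---|---|---|---|
| 8 days | 0.08 | 0.54 | 0.44 |
| 10 days | 0.10 | 0.68 | 0.55 |
| 15 days | 0.15 | 1.02 | 0.82 |
| 30 days | 0.30 | 2.03 | 1.64 |

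**Step 4: would the data reveal it?** A slope comparison fitted to 2006-2013 alone, rooms against controls, returns d exactly in this noise-free setting. Adding an adopter-specific linear slope to the full model brings the spurious effect to 0.00.

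**Step 5: what the slope model costs.** Suppose there is no prior divergence and a true effect of −1 day that builds up in equal steps over five years (assumed). For the training dates above, the average effect over post-adoption unit-years is −0.71 day, and the slope model returns −0.37. For a common 2014 adoption the average is again −0.71, and the slope model returns −0.29. The model therefore shrinks a real effect that builds gradually.

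**The case against.** The strongest reply is that a pre-trend check refines a difference-in-differences design that this plan has not yet specified, and that the missing calendar-time term is the more basic gap. That stands, and the fix takes both together. Step 2 shows why the time term alone is not enough. It can also be said that the Statistical analysis section describes what the planned analyses include, which leaves room for more. That is true, but no such analysis is pre-specified.

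A reader might infer more than the documents support:

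- *That units chose to adopt.* The allocation mechanism is not described. The Background says only that roll-out was systematic. The argument needs no more than the absence of described randomisation.
- *That the bias favours the hypothesis and comes with a narrow interval.* The direction follows the unknown trend, and a slower decline in adopters would bias the other way. With no standard deviation, intraclass correlation or sample size given, the interval width is unknown.
- *That about 2 days is the expected error, to be set against the 3.9 days cited in the Background.* The 2-day figure needs a 30-day mean stay, but the cohort is all infants needing neonatal care, and the 3.9 days refer to preterm infants.
- *That eight clean years precede adoption in both arms.* The count applies to rooms. Training dates are not in the readable text, and Figure 1, which may hold them, is not shown.
- *That an effect should count only if it survives an adopter-specific slope.* Step 5 shows that such a rule penalises gradual effects, which are plausible for staff training.

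**Conclusion.** The point holds as a limitation of the pre-specified analysis. It is not evidence of bias in the data. With the terms listed, any differential trend passes into the intervention estimate at about 7.5 times its yearly size. With birth-year added, the multiplier is still about 5.5 to 7.5. The first figure does not depend on adoption dates. The second does, and its lower end rests wholly on assumed training dates. In days, a 1% per year divergence corresponds to roughly 0.5 to 2.0 days for rooms across assumed mean stays of 8 to 30 days. Whether a divergence exists, and in which direction, is unknown. What matters is that the planned output could not show it. The change should be made before results are seen.

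**What to change.** In the Statistical analysis section:

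1. Add birth-year effects to the length-of-stay model, and state that the intervention term switches on at each unit's adoption date.
2. Pre-specify an event-time analysis: length of stay by year relative to each unit's adoption, before and after, with the 10 never-adopting units as reference, separately for training and for rooms.
3. Report the pre-adoption coefficients with intervals and a joint test. For rooms, births in 2006-2013 precede every conversion. For training, tabulate each unit's dates so that the usable pre-period is visible.
4. Show the model with an adopter-specific linear slope as a sensitivity analysis only, not as a pass/fail rule.
5. If the pre-adoption estimates show divergence, word the conclusion as an association.

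The cost is a little more analysis on register data already in scope, plus the unit adoption dates. Intervals will be wider. With only 4 room units the joint test has limited power, so a non-significant result is weak reassurance and the coefficients and intervals should carry the interpretation. The slope model will understate effects that build gradually, and the report should say so.

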## Background

In Europe, over 500,000 newborn infants are hospitalized each year. Infants are often separated from their parents during their hospitalization. One study showed that very preterm infants spent 80% of their time without any human contact (1). A European survey showed a large variation in parents' presence between hospitals, starting from 2.6 hours per day (unpublished data). Even when present, the parents are often just bystanders.(2,3) Separating the child from the parents places the socio-emotional and cognitive development at risk.(4,5) Studies have shown that parental involvement during hospitalization facilitates growth, socio-emotional, cognitive and linguistic development in preterm infants.(6-9)

An intervention directed at empowering parents shortened the length of stay by 3.9 days in preterm infants.(10) Vohr et al. showed that in settings with single-family room architecture, the infants of actively participating mothers had on average 15 days shorter length of stay compared to infants of non-active mothers. Interventions aimed at family-centered care are heterogeneous and their effects vary. In a meta-analysis comprising seven studies on family-centered care interventions, the length of stay was unaffected, but on the other hand e.g. preterm subpopulations were not considered.(11)

Parental presence can also be encouraged by hospital architecture. Even if modern hospitals nowadays include facilities also for parents based on the beneficial effects of single-family rooms (12,13), only 13.3% of 331 neonatal units provided parents with the facilities needed to stay with their infant throughout a 24-hour day.(14) Single-family rooms shortened the length of stay by 10 days among very preterm infants born before 30 gestational weeks in a randomized setting in Stockholm.(15) Also single-family room models are heterogeneous; according to a loose definition three solid walls suffices to qualify as single-family room, and does not necessarily include beds for the parents. A meta-analysis of 12 different single-family room studies did not show any significant benefit regarding length of stay compared to traditional hospital architecture.(16) However, in this meta-analysis most studies were observational studies without control groups; only one randomized study was included and no causal inferences could be drawn.

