## **Research questions**

- Does the Close Collaboration with Parents training program affect the length of stay in neonatal units?
- Does single-family room architecture affect the length of stay in neonatal units?
- Do the interventions affect the need for outpatient visits after discharge during the first year of life?
- Are the interventions cost-effective?
- Do the interventions affect early postnatal growth in preterm infants?

[figure not shown]
Our hypotheses are that the length of stay will be shorter, outpatient visits fewer and early postnatal growth better in units where either or both of these interventions have been implemented.

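### The only cost basis named for cost-effectiveness is hospitalization, so a change in first-year outpatient visits, collected on the same infants, would not reach the cost result

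*Combined protocol and SAP*

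**What the plan says.** All references are to the combined protocol and SAP.

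- **Research questions.** The economic question is unrestricted: "Are the interventions cost-effective". A separate question asks: "Do the interventions affect the need for outpatient visits after discharge during the first year of life". The stated expectation is fewer visits: "Our hypotheses are that the length of stay will be shorter, outpatient visits fewer and early postnatal growth better".
- **Outcomes.** The economic outcome is secondary and carries one cost basis: "Cost effectiveness (according to hospitalization cost analyses carried out by the Institute for Health and Welfare". Visits are listed separately, as a quantity without a price: "The amount of outpatient visits after discharge during the first year of life".
- **Methods.** Both kinds of data come from the same registers: "length of stay, growth parameters and outpatient visits will be obtained from the Hospital Discharge Register and the Medical Birth Register". They are joined for each infant: "These data will be linked through the infants' personal identification codes".
- **Statistical analysis** contains no cost model. **Timeline** says only when cost-effectiveness will be calculated. Neither gives a perspective, a time horizon or a list of cost components.

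**The concern.** Both interventions are expected to bring discharge forward. After an earlier discharge, the follow-up period is an obvious place for resource use to change, and the plan recognises this by asking about outpatient visits. The named cost basis nevertheless stops at hospitalization. The length-of-stay and visit estimates could both be correct and still never be combined into one cost per infant.

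The error can run either way. If visits fall, a hospitalization-only result misses part of the benefit. If visits rise, it credits the intervention with a saving that is partly spent in the clinic. The section on meaning and potential implications says the findings should inform how resources are allocated, so the cost result is meant to support decisions.

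**Working it through.** The plan states no cost figure, unit cost or expected visit count, so there is nothing to reproduce. The check has two parts.

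**1. Does any section bring visits into the cost outcome?** Reading every section that mentions cost, hospitalization or visits:

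| Section | Cost content | Visit content |
|---|---|---|
| Research questions | Unrestricted cost-effectiveness question | Separate question; fewer expected |
| Methods | None | Obtained from registers, linked by infant |
| Outcomes | Hospitalization cost analyses only | Separate count, no price |
| Statistical analysis | None | None |
| Timeline | Date of calculation only | None |

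No section prices visits or adds them to cost. None expressly excludes them either.

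**2. How much could it matter?**

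Inputs:
- *d*, days of stay saved per infant. Two values are cited in Background. The first is 3.9: "An intervention directed at empowering parents shortened the length of stay by 3.9 days in preterm infants". The second is 10 days, for single-family rooms in infants born before 30 weeks. A third value, 1 day, is assumed. It is included because the study population is all infants needing neonatal-unit care after birth, and the pooled effect may be smaller than in preterm infants.
- *r*, the cost of one outpatient visit divided by the cost of one neonatal bed-day. Assumed, 0.1 to 0.5.
- *v*, the change in visits per infant. Assumed to be +2 for illustration.

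Formulas, in bed-day equivalents:
- Saving booked on hospitalization alone = *d*
- Saving net of visits = *d* − *r* × *v*
- Overstatement as a share of the booked saving = *r* × *v* / *d*
- Extra visits that cancel the saving = *d* / *r*

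With *v* = +2, *r* × *v* runs from 0.1 × 2 = 0.2 to 0.5 × 2 = 1.0.

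| Days saved | Net saving (r = 0.5 to 0.1) | Overstatement (r = 0.1 to 0.5) | Cancelling visits at r = 0.1 / 0.25 / 0.5 |
|---|---|---|---|
| 1 (assumed) | 0 to 0.8 | 0.2/1 = 20% to 1.0/1 = 100% | 10 / 4 / 2 |
| 3.9 | 2.9 to 3.7 | 0.2/3.9 = 5% to 1.0/3.9 = 26% | 39 / 15.6 / 7.8 |
| 10 | 9.0 to 9.8 | 0.2/10 = 2% to 1.0/10 = 10% | 100 / 40 / 20 |

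The formula is symmetric. If visits fall by two (*v* = −2), the booked saving is too small by the same 0.2 to 1.0 bed-day equivalents, so the percentages apply as understatement.

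**The case against.** **The plan does not exclude outpatient cost.** The outcome line names a costing source and does not list components. What the Institute's analyses contain cannot be seen from the documents. A reader might infer that the sponsor has decided to value outpatient care at zero, and the text does not support that. What stands is that hospitalization is the only component specified. If more is intended, the plan has to say so before analysis, or the components could be chosen once results are known.

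**Care shifted to clinics would be booked as a saving.** This reading is tempting, but it picks one direction. No section reports that visits rise after either intervention, and the plan hypothesises that they fall. On that hypothesis the omission is conservative. The supportable statement is two-sided.

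**Not all post-discharge care is left out.** The primary outcome is limited to the initial stay, but the cost outcome refers to hospitalization without that limit, so readmissions may be covered. This is correct, and a remedy confined to the initial stay could be narrower than the plan's own wording.

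**A shift would be visible anyway.** The visit count is reported as its own outcome. That is true of the count, but it gives the reader no net cost per infant.

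**The magnitude is mostly assumption.** This stands. At the stay reductions cited in Background, only a large rise in visits would cancel the saving. The large percentages appear only at the assumed 1 day. On the other hand, the cited reductions come from preterm or very preterm infants, so they do not settle the effect in the whole study population.

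**Pricing visits does not complete the economic analysis.** The cost of the training and of the rooms is not named in the outcome either, although the plan describes such interventions as demanding of resources. That is a separate gap, and the change proposed here does not close it.

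**Conclusion.** The point holds in a limited form. The cost-effectiveness outcome has one named cost basis, hospitalization, while first-year outpatient visits are collected and linked on the same infants and never priced. As written, a change in visits does not enter the answer to the cost-effectiveness question. The resulting error is an understatement under the plan's own hypothesis and an overstatement if visits rise.

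Its size cannot be determined from the documents. The ranges in the working rest on an assumed visit-to-bed-day cost ratio of 0.1 to 0.5, an assumed change of two visits and, for the largest figures, an assumed saving of 1 day. They show that the omission is modest if the stay falls by several days and could be decisive if it falls by about one. This goes beyond missing detail, because the stated basis gives only a partial cost and the visit data for a fuller one are already in hand.

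**What to change.** In the Outcomes section, define cost per infant as the sum of:
- all hospitalization, meaning the initial stay plus first-year readmissions where the register data allow; and
- outpatient visits in the first year of life;

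with each component multiplied by its unit cost. Compare the totals between groups, report the hospitalization part as a component, and vary the unit cost of a visit in a sensitivity analysis.

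If visits cannot be priced, rename the outcome hospitalization cost and do not present it as the answer to the cost-effectiveness question.

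The change needs plan wording and a unit cost per visit, which the documents do not supply. Visit counts are already being obtained, so it needs no new recruitment or follow-up. The downside is one more cost input with its own uncertainty, which the sensitivity analysis is there to show.
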